8.4.7 Insulin dose

Subjects will be instructed in how to record their insulin treatment in the diaries. Each record should include date, time point (i.e. before breakfast, before lunch, before main evening meal) and dose of insulin.

Insulin doses will be recorded and collected on the days when three times daily SMPG are performed. The new insulin dose prescribed by the investigator at each visit/contact should be recorded in the diary.

Details regarding insulin treatment and intensification are found in Section [5.3](#) and in the titration guideline in [Appendix A](#).

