8.7 Subject compliance

Throughout the trial the investigator will remind the subjects to follow the trial procedures and requirements to ensure subject compliance. If a subject is found to be non-compliant, the investigator will remind the subject of the importance of following the instructions given including taking the trial products as prescribed. Substantial failure to comply with the prescribed dose regimen can lead to withdrawal at the discretion of the investigator. Withdrawal of subjects due to non-compliance should be discussed with monitor and or clinical research assistant (CRA) of Novo Nordisk in advance. In case of withdrawal contact the IV/WRS and perform a withdrawal session.

Treatment compliance:

The investigator must assess the treatment compliance of the subject at each visit/phone contact by evaluating the glycaemic control, the SMPG profiles and all relevant data in the subject's diary.

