The actual daily insulin dose is recorded on the three random days when 3-point SMPG are performed prior to each visit for visits 3-26. The calculated/prescribed insulin dose is recorded for visits 2-25. The actual insulin dose from the last of the three days and calculated/prescribed insulin dose will be summarized descriptively according to regimen as dose in units and units/kg per visit. Total daily dose, which is the sum of doses given before breakfast and before main evening meal for the BID treatment group, and the sum of doses given before breakfast, before lunch and before main evening meal for the TID treatment group, will also be summarized descriptively as dose in units and units/kg per visit.

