Appendix A: Biphasic insulin aspart Titration Guideline

Trial ID: BIAsp-4200

A 24-week, multinational, multicentre, randomised, open label, parallel-group treat-to-target trial to compare efficacy and safety of thrice daily versus twice daily NovoMix[®] 30 (Biphasic insulin aspart 30) in subjects with type 2 diabetes inadequately controlled with basal insulin

Table of Contents

	Page
Table of Contents	2
List of in-text tables	2
1 Introduction	3
2 Treatment regimens	4
2.1 Injection area.....	4
2.2 Time of injection.....	4
3 Initiation and titration of BIAsp 30	5
3.1 Initiation of BIAsp 30.....	5
3.2 Titration of BIAsp 30.....	5
3.3 Deviations from the algorithm.....	6
4 Data collection	7
5 Review procedure	8
6 References	9

List of in-text tables

	Page
Table 1 Time-point of SMPG measurement and BIAsp 30 BID dose adjustment.....	5
Table 2 Time-point of SMPG measurement and BIAsp 30 TID dose adjustment.....	6
Table 3 Increase of pre-meal dose of BIAsp 30.....	6
Table 4 Decrease of pre-meal dose of BIAsp 30.....	6

1 Introduction

The goal of insulin therapy is to achieve near normoglycaemia, i.e. to reach a pre-defined HbA_{1c} level with a low rate of hypoglycaemic episodes and as little weight gain as possible. Several trials have shown that this is difficult to achieve, unless plasma glucose (PG) values are intensively monitored and the insulin dose(s) frequently adjusted¹⁻⁷.

To ensure treatment uniformity between the sites, as well as to ensure that subjects receive an optimal treatment, titration algorithms have been developed specifying recommended dose adjustments at different PG levels.

It is recognised that treatments differ between different regions and countries. Likewise, specific titration guidelines may not be applicable in certain clinical situations. It is important that other information, such as symptoms of hypo/hyperglycaemia, previous response to dose adjustments, other glucose measurements and other indicators of the subject's level of glycaemic control, is taken into consideration when decisions on dosing are made. The investigator should always use his clinical judgement to avoid safety hazards. The investigator is responsible for the treatment of the subjects and can therefore overrule the guideline.

To optimise and maintain glycaemic control, the Investigator should, throughout the trial be at least in weekly contact with the subjects to assist the subjects in adjusting insulin doses and to ensure the subject's welfare.

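### Total daily insulin dose in the BID arm is defined without any lunch dose, although lunch doses can be recorded in both arms, and no planned table shows how well the two regimens stayed separate

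*Combined protocol and SAP*

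**What the plan says.** Section 4.2.2.1 lists total daily insulin dose as a supportive secondary safety endpoint. Section 17.4.1.2 defines it separately by arm: for BID it is "the sum of doses given before breakfast and before main evening meal for the BID treatment group", and for TID it is the breakfast, lunch and evening doses together. The same paragraph takes the actual dose from the last of the three recorded days and states that this and the "calculated/prescribed insulin dose will be summarized descriptively according to regimen as dose in units and units/kg per visit".

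The records behind the endpoint are not arm-specific. Section 8.4.7 states: "Each record should include date, time point (i.e. before breakfast, before lunch, before main evening meal) and dose of insulin". It adds: "Insulin doses will be recorded and collected on the days when three times daily SMPG are performed". Section 4 of Appendix A asks for date, dose and time point of BIAsp 30 administration to be entered in the eCRF for all subjects, but lets the investigator and sponsor agree a reduced transcription for an individual subject.

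Section 17 plans no summary of lunch doses taken in the BID arm or missed in the TID arm. Section 17.2 analyses safety data as treated, with no rule for a subject who takes the other arm's regimen.

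**The concern.** A total should count everything that was recorded as given. Here the rule for one arm fixes in advance which injections may count. If a BID subject records a lunch dose, the reported total is too low for that subject, the BID mean is too low, and the difference in dose between TID and BID is overstated by the same amount.

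Such a dose is possible, though the documents neither foresee it nor give a rate. The trial is open-label, both arms use the same pen, all subjects must be able and willing to eat three main meals, and BID subjects measure glucose before lunch.

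The second part of the concern is interpretation. The lunch injection is the one injection that distinguishes the regimens. If the HbA1c difference turns out small, a reader will want to know whether BID subjects took lunch doses and TID subjects skipped them. The data to answer this are largely collected, but no planned output presents them.

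**Working it through.** **Inputs.** The dose definitions and the visits covered (3 to 26) come from section 17.4.1.2; the recording rule from sections 8.4.7 and 8.6.2; the eCRF rule from Appendix A, section 4; the sample-size inputs from section 17.1. The plan gives no figure for insulin dose, so there is none to reproduce on this endpoint.

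**Step 1: apply the definition.** Let B, L and E be the recorded breakfast, lunch and evening doses on the day used.

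| Subject | Recorded that day | Reported total | Shortfall |
|---|---|---|---|
| BID, as planned | B + E | B + E | 0 |
| BID, with a lunch dose | B + L + E | B + E | L |
| TID, as planned | B + L + E | B + L + E | 0 |
| TID, lunch dose omitted | B + E | B + E | 0 |

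Only the second row goes wrong. An omitted TID lunch dose already lowers the TID total, as it should.

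**Step 2: size in the BID mean.** If a share s of BID subjects has a lunch dose on the day used, with mean L, the BID mean is understated by s × L. Neither value is in the documents. Assuming s = 10–20% and L = 10–16 U:

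- low end: 0.10 × 10 U = 1.0 U
- high end: 0.20 × 16 U = 3.2 U
- if no BID subject takes a lunch dose: 0

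**Step 3: what the lunch-dose table could use.** Visits 3 to 26 are 24 contacts. With three recorded days before each, a completing subject has up to 24 × 3 = 72 recorded days out of 24 × 7 = 168, or 43%. Section 8.6.2 adds the first and last day of treatment. Lunch doses on other days would not be seen.

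**Step 4: does the primary analysis move?** A two-sample t calculation with difference 0.3%, SD 1.1%, two-sided 5% and 1:1 allocation gives 213 per arm, 426 in total, with power 80.2%. This reproduces the plan's figure. Insulin dose is not an input to that calculation, and it is not a term in the MMRM of section 17.3. If a share c of BID subjects took lunch doses and gained the whole TID effect, the expected difference would be 0.3 × (1 − c), for example 0.285% at c = 5% and 0.24% at c = 20%. These shares are assumptions, and the result is the same whichever way total daily dose is defined.

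**The case against.** The strongest reply is that a BID lunch dose would be a protocol deviation, and the plan already has ways to catch it. Section 5.3.1 fixes the injection times. Appendix A does say "The investigator is responsible for the treatment of the subjects and can therefore overrule the guideline", but the context is dose adjustment at given glucose levels, not the number of injections. Diary doses are source data (section 14.1), titration data go to the eCRF within 24 hours on work days with reasons for deviating from the algorithm, the sponsor's titration group reviews them after each contact (section 14.2), and deviations must be documented (section 19). A subject who consistently takes three injections may also be counted under TID by the as-treated rule, and the lunch dose would then be summed.

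Most of this stands, and it rules out stronger readings that a reader might reach:

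- **That crossover is hidden.** It is not: lunch doses can be recorded, entered and reviewed centrally. They are only left out of the total and not tabulated.
- **That the arms differ only in the lunch injection.** They do not. Section 5.2 says the titration algorithms differ, and in Appendix A the breakfast dose follows the pre-lunch value in TID but the value before the evening meal in BID.
- **That adherence is inferred from the outcome.** Section 8.7 has compliance assessed "by evaluating the glycaemic control, the SMPG profiles and all relevant data", and the sentence goes on to name the subject's diary, which holds the dose records. Glycaemic control is one source among three.
- **That using the last of three days is an error.** Under weekly titration it is a reasonable snapshot of the current dose.

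What the reply does not remove is the definition itself. Central surveillance follows up individual deviations; it is not a planned result. The as-treated rule is not spelled out, and it would not help with occasional lunch doses in a subject who remains in the BID group. The planned actual-dose summary by regimen does not say whether a BID lunch dose would appear in it.

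**Conclusion.** The point holds as a minor one. As written, any recorded lunch dose in a subject analysed as BID is dropped from total daily insulin dose, and no planned output describes the separation of the regimens at lunch. The error in an affected subject is the whole lunch dose. The error in the BID mean depends on a frequency that the documents do not give; the 1.0–3.2 U range rests entirely on the assumed shares and doses, and the true figure could be zero.

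The effect reaches one descriptive safety endpoint and the interpretation of the regimen comparison. A reader might infer that the primary comparison or its power is compromised by the dose definition. The documents do not support that: the primary analysis is as randomised, insulin dose is not in the model, and any dilution of the HbA1c difference by crossover would arise under either definition.

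**What to change.** In section 17.4.1.2, define total daily dose in both arms as the sum of all BIAsp 30 doses recorded on the day used for the summary. From the same records, add one table by arm and visit giving the percentage of recorded days with a lunch dose taken (BID) or omitted (TID), with the number of subjects and recorded days as denominators. State whether arm means randomised or as treated; the randomised arm is the one that describes separation of the regimens.

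The cost is one changed sentence and one table. No new data are collected. The table covers recorded days only and will be incomplete for subjects with an agreed reduced transcription, which a footnote should say. The compliance assessment in section 8.7 and the choice of day need no change for this point.

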17.5 Patient reported outcomes

Diabetes Treatment Satisfaction Questionnaire (status): DTSQs

The DTSQs is a self-completion questionnaire used to investigate the subject's treatment satisfaction and will be completed at Visit 2 and Visit 26. The eight items in the DTSQs are scored on a scale from 0 to 6. Overall treatment satisfaction is defined as the sum of items 1, 4, 5, 6, 7, and 8. The DTSQs scores at baseline and at end-of-treatment will be summarized descriptively. Change from baseline to end-of-treatment will be calculated and summarized.

18 Ethics

The trial will be conducted in compliance with ICH GCP¹, applicable regulatory requirements, and in accordance with the Declaration of Helsinki².

At the termination of the trial, the subject will consult their investigator to decide on the best available marketed treatment.

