4.1 Objectives

Primary objective

To compare the efficacy of thrice daily BIAsp 30 versus twice daily BIAsp 30, both in combination with metformin, in subjects with type 2 diabetes inadequately controlled on basal insulin combined with OADs.

Secondary objectives

- To compare safety of thrice daily BIAsp 30 versus twice daily BIAsp 30, both in combination with metformin, in subjects with type 2 diabetes inadequately controlled on basal insulin combined with oral anti-diabetic drugs (OADs)
- To compare patient reported treatment satisfaction of thrice daily BIAsp 30 versus twice daily BIAsp 30

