8.1.7 Withdrawn subjects

If a subject is withdrawn from the trial, the investigator must aim to undertake procedures similar to those for Visit 26 as soon as possible. The subject should also have the follow-up contact performed, if possible. The subjects should be requested to return all used, partly used and unused trial product.

The end-of-trial form must be completed, and final drug accountability must be performed even if the subject is not able to come to the trial site. A withdrawal session must be made in the IV/WRS. The case book must be signed.

Although a subject is not obliged to give his/her reason(s) for withdrawing from a trial, the investigator must make a reasonable effort to ascertain the reason(s), while fully respecting the subject's rights. Where the reasons are obtained, the primary reason for not completing the trial must be specified on the end-of-trial form in the eCRF.

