8.6 Other assessments

8.6.1 Patient-reported outcome questionnaire

The PRO questionnaire of DTSQs will be collected at Visit 2 and Visit 26. The questionnaire is self-administered and must be completed by the subject without any assistance from the site staff or anyone else, prior to any other trial related activities during the designated visits. The estimated average subject completion time is 5 minutes.

Review of PRO questionnaires by investigator or delegated staff must be documented either on the documents and/or in the subject's medical record. This includes ensuring that any potential adverse events (AEs), any overall changes in health and concomitant medication, are reported.

If clarification of entries or discrepancies in the PRO questionnaires is needed, the subject must be questioned and a conclusion made in the subject's medical record. Care must be taken not to bias the subject.

Data from the PRO questionnaires will be transferred into the eCRF by the investigator or delegated staff.

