17.4.1.2 Safety endpoints

All safety endpoints will be summarised and analysed using the safety analysis set. Unless otherwise specified safety endpoints will be analysed by descriptive statistics only.

Adverse events

All AEs will be coded using the most recent version of the MedDRA coding. A TEAE is defined as an event that has onset date (or increase in severity) on or after the first day of exposure to trial product and no later than 7 days after the last day on trial product.

TEAEs are summarised descriptively and displayed in terms of the number of subjects with at least one event (N), the percentage of subjects with at least one event (%), the number of events (E) and the event rate per 1000 years of exposure (R)

Summaries of TEAEs and of serious TEAEs will be presented as an overview including all AEs, serious AEs, number of deaths, AEs by severity, AEs by relation to treatment and AEs leading to withdrawal.

Furthermore summary tables based on system organ class and preferred terms are made for:

- All TEAEs
- Serious TEAEs
- Possibly or probably related TEAEs
- Severe, moderate and mild TEAEs
- TEAEs with preferred term that are experienced by at least 5% of the subjects in any treatment arm or by at least 5% of all subjects
- TEAEs leading to withdrawal

Definition of Hypoglycaemia

Treatment emergent: hypoglycaemic episodes will be defined as treatment emergent if the onset of the episode occurs on or after the first day of trial product administration, and no later than 7 days after the last day on trial product.

Nocturnal hypoglycaemic episodes: are episodes with time of onset between 00:01 and 05.59 both inclusive.

[figure not shown]
Hypoglycaemic episodes are classified according to the Novo Nordisk classification of hypoglycaemia (see [Figure 17–1](#)) and the ADA classification of hypoglycaemia (see [Figure 17–2](#)).

Novo Nordisk classification of hypoglycaemia

In normal physiology, symptoms of hypoglycaemia occur below a plasma glucose level of 3.1 mmol/L (56 mg/dL)²¹. Therefore, Novo Nordisk has included hypoglycaemia with plasma glucose levels below this cut-off point in the definition of blood glucose (BG) confirmed hypoglycaemia.

Novo Nordisk uses the following classification in addition to the ADA classification:

- Severe hypoglycaemia according to the ADA classification²².

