The number of treatment emergent severe or BG confirmed hypoglycaemic episodes will be analysed by a negative binomial regression model with a log-link function and the logarithm of the time period in which the hypoglycaemic episodes are considered treatment emergent as offset. The model will include treatment, combination of the two stratification factors and region as factors. The results will include the 95% confidence interval for the event rate ratio (BIAsp TID over BIAsp BID) and p-value as part of the presentation. To the extent where data allow, analyses will be performed on all severe or BG confirmed episodes and nocturnal severe or BG confirmed episodes separately.

Vital signs

Vital signs (systolic blood pressure, diastolic blood pressure and pulse) will be summarised and tabulated by treatment and visit together with the change from the baseline to end-of-treatment.

Laboratory assessments

All continuous laboratory parameters will be evaluated by descriptive statistics and tabulated by visit together with change from baseline to end-of-treatment. Shift tables showing changes from baseline to end-of-treatment (normal and abnormal) will be constructed for each laboratory safety variable. No formal statistical analyses of laboratory parameters will be performed and abnormal values will be listed.

Eye examination and physical examination

For eye examination and physical examination, a shift table for change from baseline to end-of-treatment will be generated. Subjects with any change in examination result will be listed.

Change in body weight after 24 weeks of treatment

Change from baseline in body weight after 24 weeks of treatment will be analysed with a similar method as the primary endpoint, where baseline body weight will replace baseline HbA_{1c} in the model.

Total daily insulin dose

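### The plan sets out to compare treatment satisfaction between the arms, but Section 17.5 provides no between-arm estimate for it

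*Combined protocol and SAP*

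**What the plan says.** Section 4.1 lists one primary and two secondary objectives. The second secondary objective reads: "To compare patient reported treatment satisfaction of thrice daily BIAsp 30 versus twice daily BIAsp 30". Section 4.2.2.1 gives it an endpoint, change from baseline in the DTSQs after 24 weeks. That endpoint is filed as a supportive secondary health economics endpoint and lacks the asterisk that marks key endpoints.

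On collection, Section 8.6.1 says: "The PRO questionnaire of DTSQs will be collected at Visit 2 and Visit 26". There is therefore one baseline and one post-baseline score.

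On analysis, Section 17.5 defines overall satisfaction as the sum of items 1, 4, 5, 6, 7 and 8, each scored 0 to 6. It then says "The DTSQs scores at baseline and at end-of-treatment will be summarized descriptively" and "Change from baseline to end-of-treatment will be calculated and summarized". It names no model, treatment difference, confidence interval or analysis set.

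Section 17 allows, but does not require, a separate SAP finalised before database lock. No separate SAP text is among the documents supplied.

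**The concern.** An objective worded as a comparison calls for an estimate of the difference and its uncertainty. Section 17.5 stops at summaries. If the text is followed as written, the report need not contain a treatment difference in satisfaction. If one is produced, its form (final score or change, adjusted or not, which subjects) would be chosen without pre-specification.

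That matters somewhat more here than for a routine questionnaire. The regimens differ by one injection a day, Section 3.2 names simplicity of use as something health care providers look for, and the trial is open-label (Section 5.2). A self-reported score collected without blinding gains from having its analysis fixed in advance.

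**Working it through.** **1. Each objective against its planned between-arm estimate**

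| Objective (Section 4.1) | Planned estimate |
|---|---|
| Efficacy (primary) | MMRM difference at week 24 with 95% CI (17.3) |
| Safety (secondary) | Rate ratio with 95% CI for severe or BG confirmed hypoglycaemia; modelled change in body weight (17.4.1.2) |
| Treatment satisfaction (secondary) | None (17.5) |

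Low rank alone does not explain the gap. Body weight is also supportive and not key, yet: "Change from baseline in body weight after 24 weeks of treatment will be analysed with a similar method as the primary endpoint".

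**2. Whether a general rule fills the gap**

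- Section 17.4.1.1 extends the primary-endpoint method to other continuous endpoints, but only those in its own efficacy list. The DTSQs is not on it.
- The presentation rule at the start of Section 17 (means, difference, CI, p-value) applies to endpoints analysed by MMRM. No MMRM is planned for the DTSQs.
- The default "Unless otherwise specified safety endpoints will be analysed by descriptive statistics only" is confined to safety endpoints, so it is not a stated choice for the DTSQs.

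**3. The trial's own sizing figure**

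The plan gives no DTSQs figure. Its only sizing figure, 426 in total for HbA1c (difference 0.3, SD 1.1, two-sided 5%, 80% power), reproduces. The noncentral t gives power 0.79998 at 212 per arm and 0.8018 at 213 per arm. The point made here does not depend on it.

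**4. Precision of a DTSQs difference**

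Unadjusted 95% half-width = t(0.975, 2n − 2) × sqrt(2/n), in SDs of the outcome.

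- 340 expected completers (Section 6.1), n = 170: 1.967 × 0.1085 = 0.213 SD.
- All 426, n = 213: 1.966 × 0.0969 = 0.190 SD.

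The total runs from 0 to 6 × 6 = 36. The documents give no DTSQs SD. If the SD of change is assumed to be 5 to 8 points, the half-width is 1.07 to 1.71 points with 340 subjects and 0.95 to 1.52 points with 426.

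**5. What baseline adjustment would add**

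Assume equal variances at both visits and a baseline-to-final correlation rho (not given in the documents). In units of the single-visit SD, the half-width at 170 per arm is 0.213 multiplied by:

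- final score: 1
- change score: sqrt(2(1 − rho))
- ANCOVA: sqrt(1 − rho²)

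| rho | Final | Change | ANCOVA | Final ÷ ANCOVA | Change ÷ ANCOVA | Better one is wider by |
|---|---|---|---|---|---|---|
| 0.3 | 0.213 | 0.252 | 0.204 | 1.048 | 1.240 | about 5% |
| 0.5 | 0.213 | 0.213 | 0.185 | 1.155 | 1.155 | about 15% |
| 0.7 | 0.213 | 0.165 | 0.152 | 1.400 | 1.085 | about 8% |

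Any further gain from adjusting for strata and region is ignored.

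**6. Who would contribute**

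426 − 340 = 86 subjects, or 86/426 = 20%, are expected not to complete. For them Section 8.1.7 says "the investigator must aim to undertake procedures similar to those for Visit 26 as soon as possible", and Section 18.4 says that end-of-trial visit data are used for the report. No line says whether a questionnaire completed at such a visit enters the DTSQs analysis. The no-imputation default in Section 17 is stated for efficacy variables.

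**The case against.** The best defence is that a descriptive comparison is a legitimate choice for this endpoint. It is supportive, labelled health economics, not key, and its objective is absent from the key secondary objectives in the Section 1 summary. Much of the safety objective (adverse events, vital signs, laboratory tests, eye examination, insulin dose) is also served by description alone. A SAP could have added detail. This stands as an argument for low priority. It does not remove the mismatch between the verb in 4.1 and the method in 17.5. It does mean that rewording the objective would resolve the mismatch as well as adding a model would.

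Two stronger readings are tempting, and the documents do not support them.

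- *That the summaries might be pooled over arms.* Section 17.5 does not say by arm, whereas vital signs "will be summarised and tabulated by treatment and visit together with the change from the baseline to end-of-treatment". But the laboratory, eye and physical examination and adverse event text in 17.4.1.2 also leaves the arm unstated. This is a drafting habit, and in a two-arm trial whose objective names both arms, by-arm tables are the natural reading.
- *That a reader left with summaries loses up to 24% in interval width.* That figure (rho = 0.3) supposes that only change scores are available. Section 17.5 also summarises end-of-treatment scores, which under randomisation estimate the same difference. Using the better of the two, the loss at rho = 0.3 is about 5%.

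The withdrawal-visit question is smaller and not specific to the DTSQs, since Section 8.1.7 covers all Visit 26 procedures. It matters here only because any added analysis must say which scores it uses.

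**Conclusion.** The mismatch is real and minor. Satisfaction is the only objective in Section 4.1 without a planned between-arm estimate, and no other rule in Section 17 supplies one. The cost in precision is modest: about 5% to 15% in interval width over the assumed correlations of 0.3 to 0.7, given equal variances and by-arm means, SDs and counts. The larger loss is that no estimate is pre-specified and none is committed to the report.

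It would be wrong to infer that the objective cannot be addressed at all, since an unadjusted interval could be derived from by-arm tables. Nothing here touches the primary analysis, the sample size or the key endpoints. The change is worth making because it is cheap, and it is optional.

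**What to change.** Add to Section 17.5, or to a SAP finalised before database lock, wording to this effect:

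> Change from baseline to Visit 26 in the DTSQs total (items 1, 4, 5, 6, 7, 8) will be analysed by ANCOVA with treatment, combination of the two stratification factors and region as factors and baseline DTSQs total as covariate. The analysis uses FAS subjects with a baseline and a Visit 26 score. The TID minus BID difference will be given with its 95% CI, as a supportive result to be interpreted in light of the open-label design. A sensitivity analysis will also include questionnaires completed at the withdrawal visit (Section 8.1.7).

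With a single post-baseline score, no repeated-measures model is needed. Naming the contributing subjects matters. About 340 of 426 are expected to have a Visit 26 score, and Section 17.2 ties the FAS to the ITT principle, so a bare reference to the FAS would present a largely completer analysis as something broader. Keep the descriptive summaries; adding that they are by arm takes a few words.

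The cost is a few sentences, one extra model and its sensitivity run, with no new data and no burden on subjects. The drawback is a supportive estimate that rests largely on completers.

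If the sponsor does not want an estimate, the alternative is to reword the objective in Section 4.1 as descriptive.
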